14.1.4.4.1 Head and neck by cohort, stage of disease and overall (mITT)

14.1.4.4.2 Thorax by cohort, stage of disease and overall (mITT)

14.1.4.4.3 Abdomen by cohort, stage of disease and overall (mITT)

14.1.4.4.4 Lower limbs by cohort, stage of disease and overall (mITT)

14.1.4.4.5 Skin by cohort, stage of disease and overall (mITT)

14.1.4.5: Neurological examination at baseline

14.1.4.5.1. Psychiatric observation by cohort, stage of disease and overall (mITT)

14.1.4.5.2. Higher functions by cohort, stage of disease and overall (mITT)

14.1.4.5.3. Cranial nerves by cohort, stage of disease and overall (mITT)

- 14.1.4.5.4. Mobility by cohort, stage of disease and overall (mITT)
- 14.1.4.5.5. Motor coordination and balance by cohort, stage of disease and overall (mITT)
- 14.1.4.5.6. Primitive reflex by cohort, stage of disease and overall (mITT)
- 14.1.4.5.7. Sensitivity by cohort, stage of disease and overall (mITT)
- 14.1.4.5.8. Other neurological abnormalities by cohort, stage of disease and overall (mITT)

#### 14.1.4.6: HAT diagnosis (examination of blood, lymph and CSF samples) at baseline

- 14.1.4.6.1. Blood tests and lymph node aspirate examination by cohort, stage of disease and overall (mITT)
- 14.1.4.6.2. Examination of cerebrospinal fluid by cohort, stage of disease and overall (mITT)

#### **14.1.5 Medical history**

- 14.1.5.1: Medical history by MedDRA SOC and PT, by stage of disease and overall (mITT)
- 14.1.5.2: Medical history by MedDRA SOC and PT, by cohort and overall (mITT)

#### **14.1.6 Prior and concomitant therapies**

- 14.1.6.1: Prior therapies by therapeutic class (ATC2) and WHO-DD preferred name, by stage of disease and overall (mITT)
- 14.1.6.2: Prior therapies by therapeutic class (ATC2) and WHO-DD preferred name, by cohort and overall (mITT)
- 14.1.6.3: Concomitant therapies by therapeutic class (ATC2) and WHO-DD preferred name, by stage of disease and overall (mITT)
- 14.1.6.4: Concomitant therapies by therapeutic class (ATC2) and WHO-DD preferred name, by cohort and overall (mITT)

#### **14.1.7 Extent of exposure and treatment compliance**

- 14.1.7.1: Treatment compliance by cohort, stage of disease and overall (mITT)

#### **14.1.8 Analysis of potential biases**

##### **14.1.8.1: Demographic data by cohort, stage of disease and overall**

Same outputs as above on Treated set

Same outputs as above on Set of patients not treated but with least one blood test or lymph node aspirate test positive

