**Figure 2. Decision Tree for the Diagnosis of HAT in the Context of the Study**

\*Preferably CATT for active screening and RDT for passive screening

\*\*Preferably in the following order: mAECT-BC (passive); mAECT (active); CTC/Woo test; Thick blood smear

CATT: Card Agglutination Test for Trypanosomiasis

Tryps: Trypanosomes

CSF: Cerebrospinal Fluid

WBC: White Blood Cell count

Pos: Positive

Neg: Negative

Screening, which consists in investigation of potential infection, will be performed by assessing clinical signs, including the presence of swollen cervical lymph nodes, and by serological tests. In the community or at hospital, serological screening will be performed using a rapid diagnostic test (RDT) or the card agglutination test for trypanosomiasis (CATT) (9).

For patients with a positive result on serological screening, tests to detect the parasite will be performed, preferably using one of the concentration methods that allow for microscopic detection of motile parasites in fresh centrifugated samples. The testing will be performed on lymph node aspirate collected by needle biopsy and in the blood, using the Woo test (capillary tube centrifugation) or the mini-anion exchange centrifugation test (mAECT) (3) or, if concentration methods are not available, by examination of a thin blood smear or stained thick blood smear.

In the context of the study, the improved technique, called the “mini-anion exchange centrifugation test on buffy coats” (mAECT-BC) (4), will be used whenever possible in patients with positive serological tests and negative findings on the usual parasitological tests.

Because the serological tests currently available are not 100% reliable, an individual may have negative serological tests, but still show clinical signs suggestive of HAT. In this case, the individual will undergo the parasitological tests described above.

Current therapeutic options are not the same for early- and late-stage HAT and, as a result, before initiating treatment, it is necessary to determine the stage of the disease by analysing CSF collected on lumbar puncture. In usual practice, late-stage HAT is confirmed by the presence of parasites and/or of a CSF WBC above 5/ $\mu$ L. However, in clinical studies assessing treatments for late-stage HAT, the WHO recommends that a CSF WBC of 20/ $\mu$ L should be used as the threshold for determination of late-stage HAT (23). A CSF WBC of 20/ $\mu$ L will therefore be used as the threshold in this study.

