## 8.12. Analysis of potential biases

In order to assess a potential selection bias, descriptive statistics will be provided on all patients treated and on all patients NOT treated (but with a confirmation of the presence of trypanosomes in any body fluid) for:

- Demographic data
- Vital signs at baseline
- Clinical signs and symptoms of HAT at baseline
- Physical examination at baseline
- Neurological examination at baseline
- HAT diagnosis (i.e. examination of blood, lymph and CSF samples)

This analysis will be performed if at least 5 % of screened patients are not included in the study.

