### 9.2.10. HAT diagnosis (examination of blood, lymph and CSF samples) at baseline

#### 9.2.10.1. Blood tests and lymph node aspirate examination

|                                    | Stage 1
(N=XX) | Intermediate
(N=XX) | Stage 1 and
Intermediate
(N=XX) | Stage 2
(N=XX) | Total
(N=XX) |
|------------------------------------|-------------------|------------------------|---------------------------------------|-------------------|-----------------|
| At least one test positive  |                   |                        |                                       |                   |                 |
| Non-missing                        | XX                | XX                     | XX                                    | XX                | XX              |
| Missing                            | XX                | XX                     | XX                                    | XX                | XX              |
| Yes                                | XX (XX.X%)        | XX (XX.X%)             | XX (XX.X%)                            | XX (XX.X%)        | XX (XX.X%)      |
| No                                 | XX (XX.X%)        | XX (XX.X%)             | XX (XX.X%)                            | XX (XX.X%)        | XX (XX.X%)      |
| Serology (CATT)             |                   |                        |                                       |                   |                 |
| Non-missing                        | XX                | XX                     | XX                                    | XX                | XX              |
| Missing                            | XX                | XX                     | XX                                    | XX                | XX              |
| Positive                           | XX (XX.X%)        | XX (XX.X%)             | XX (XX.X%)                            | XX (XX.X%)        | XX (XX.X%)      |
| Negative                           | XX (XX.X%)        | XX (XX.X%)             | XX (XX.X%)                            | XX (XX.X%)        | XX (XX.X%)      |
| Not done                           | XX (XX.X%)        | XX (XX.X%)             | XX (XX.X%)                            | XX (XX.X%)        | XX (XX.X%)      |
| CATT dilution               |                   |                        |                                       |                   |                 |

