| <same as for Serology (CATT)>      |                   |                        |                                       |                   |                 |
| mAECT-BC                    |                   |                        |                                       |                   |                 |
| <same as for Serology (CATT)>      |                   |                        |                                       |                   |                 |
| Rapid diagnostic test (RDT) |                   |                        |                                       |                   |                 |
| <same as for Serology (CATT)>      |                   |                        |                                       |                   |                 |

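### The selection-bias tables (SAP outputs 14.1.8.1 to 14.1.8.6) filter untreated patients on a positive blood or lymph node test, but SAP 8.12 defines them by trypanosomes in any body fluid

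*SAP*

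**What the plan says.** SAP 8.12 (Analysis of potential biases) sets treated patients beside "all patients NOT treated (but with a confirmation of the presence of trypanosomes in any body fluid"). It covers demographics, vital signs, clinical signs and symptoms of HAT, physical and neurological examination, and HAT diagnosis. It is run if at least 5% of screened patients are not included.

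SAP 9.1.1 lists the matching outputs, 14.1.8.1 to 14.1.8.6. Each is produced once on the Treated set and once on a second set, worded identically all six times: "Same outputs as above on Set of patients not treated but with least one blood test or lymph node aspirate test positive".

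SAP template 9.2.10.1 has nearly the same name, "Blood tests and lymph node aspirate examination". Its first row is "At least one test positive". Below that row, CATT serology and the rapid diagnostic test stand beside the parasite tests (lymph node aspirate, smear, thick smear, CTC/Woo, mAECT, mAECT-BC). The CSF result has its own template, 9.2.10.2.

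Protocol 1.3 gives serology a screening role: "serological screening will be performed using a rapid diagnostic test (RDT) or the card agglutination test for trypanosomiasis (CATT"). Parasite detection follows, and only patients whose parasites are confirmed at the investigational centre are included. For late-stage patients, Protocol 4.2 accepts the parasite in blood, lymph or CSF, singly or together.

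**The concern.** The analysis text and the output list define the same comparison group differently, and SAP section 11 (changes from the protocol) does not reconcile them. A programmer works from the output list, so the narrower or looser filter is the one likely to be coded.

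The comparison exists to show whether treated patients differ from confirmed cases who were not treated. It serves that purpose only if the untreated column holds confirmed cases, and all of them. This matters in a single-arm study with no formal success rule, where SAP 8.7 leaves the result to be read against literature and historical data.

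**Working it through.** The plan states no figure for this point, so there is none to reproduce. The check compares the two definitions over every possible pattern of results in an untreated patient.

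**Inputs**
- B: trypanosomes seen in blood or lymph (Protocol 4.2; parasite tests in SAP 9.2.10.1).
- C: trypanosomes seen in CSF (Protocol 4.2; SAP 9.2.10.2).
- S: positive CATT or RDT (screening tests in Protocol 1.3; listed in SAP 9.2.10.1).

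**Rules**
- SAP 8.12: in the set if B or C.
- Outputs 14.1.8, narrow reading (parasite tests only): in the set if B.
- Outputs 14.1.8, wide reading (every test in template 9.2.10.1): in the set if B or S.

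| B | C | S | 8.12 | Narrow | Wide |
|---|---|---|---|---|---|
| no | no | no | out | out | out |
| no | no | yes | out | out | **in (wrong)** |
| no | yes | no | in | **out (wrong)** | **out (wrong)** |
| no | yes | yes | in | **out (wrong)** | in |
| yes | any | any | in | in | in |

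The last row stands for four of the eight patterns, and all definitions agree on them.

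**Result**
- Narrow reading: two patterns are misclassified. Every patient confirmed in CSF alone is dropped, whatever the serology. Nobody unconfirmed enters.
- Wide reading: two patterns are misclassified. Seropositive patients with no parasite in any fluid enter, and CSF-only patients with negative serology are dropped. CSF-only patients with positive serology stay in.
- The pattern misclassified under both readings is CSF-only with negative serology. The protocol allows for it: "Because the serological tests currently available are not 100% reliable, an individual may have negative serological tests" and, if clinical signs suggest HAT, still go on to parasite testing.

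**Does anything else in the SAP close the gap?** The screened set in SAP section 5 is described as HAT-positive patients who consented. It does not say which test makes a patient positive, SAP 8.1 glosses the set simply as patients who gave consent, and outputs 14.1.8 do not refer to it. It might limit the entry of unconfirmed patients, but it cannot be relied on to do so. It does nothing for CSF-only patients who fail the blood or lymph filter.

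**The case against.** The best case for leaving this alone has five parts.

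1. *The wide reading is an inference.* Outputs 14.1.8 neither mention serology nor cite template 9.2.10.1, and SAP 9.2 says the templates were built from CRF labels, so CATT and RDT may appear there only because they share a CRF page. This stands. The wide reading is possible, not established. The narrow reading still departs from 8.12.

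2. *CSF-only cases may be very few.* SAP Table 2 shows blood or lymph as positive in every row, so the authors may not have expected them. This also stands as to size. But Protocol 4.2 admits such patients, and SAP Table 1 stages on CSF findings alone and puts every CSF-positive patient in Stage 2, the primary cohort.

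3. *Unconfirmed patients would be visible.* Output 14.1.8.6 tabulates each test separately for the untreated set. This helps in part: counts per test do not say how many patients had no positive parasite test, and patients removed by the filter do not appear at all.

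4. *There are other safeguards.* A reader might infer that this is the only planned check on selection. The documents do not support that. SAP 8.6.1.4 outlines NECT comparisons adjusted for baseline CSF white cells or a propensity score, if the other trials' databases can be obtained. Protocol 9.4 plans a baseline table for each NECT study, and SAP 8.1 reports reasons for non-treatment. These address related questions and do not replace the comparison of treated with untreated confirmed cases.

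5. *The table is descriptive and conditional.* It carries no test and no decision rule. This stands and limits the weight of the point.

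**Conclusion.** The contradiction is real, and the listed set is not the 8.12 set on either reading of blood test. What goes wrong depends on the reading: loss of all CSF-only patients on the narrow one; entry of seropositive patients without parasites, and loss of seronegative CSF-only patients, on the wide one.

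Two stronger conclusions are tempting and should not be drawn. The first is that the tables both admit unconfirmed patients and lose all CSF-only patients. These errors belong to opposite readings and would coincide only if every CSF-only patient were negative on both CATT and RDT, which nothing in the documents suggests. The second is that the untreated column is pushed towards milder disease. That assumes CSF-only cases are worse, and unconfirmed ones milder, on the tabulated variables, and the documents give no data on either.

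The size is unknown, because no counts by test result are given for untreated patients. A patient positive in CSF and also in blood or lymph is unaffected. The consequence is limited to a conditional, descriptive check of selection; the primary success rate and its interval do not change.

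**What to change.** In outputs 14.1.8.1 to 14.1.8.6, replace the second set with the one in SAP 8.12, spelled out: patients not treated in whom trypanosomes were seen in blood, lymph or CSF, by lymph node aspirate, smear, thick smear, CTC/Woo, mAECT, mAECT-BC or CSF examination. Add that a positive CATT or RDT alone does not qualify a patient.

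The cost is one change of SAP wording, repeated in six output titles, and a changed filter. No new data are needed: Protocol 11.7 requires a CRF for every consenting patient, and Protocol 6.2.2 places the parasite tests and the staging CSF sample at screening.

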##### **14.1.8.2: Vital signs at baseline by cohort, stage of disease and overall**

Same outputs as above on Treated set

Same outputs as above on Set of patients not treated but with least one blood test or lymph node aspirate test positive

**14.1.8.3: Clinical signs and symptoms of HAT at baseline by cohort, stage of disease and overall**

Same outputs as above on Treated set

Same outputs as above on Set of patients not treated but with least one blood test or lymph node aspirate test positive

**14.1.8.4: Physical examination at baseline**

Same outputs as above on Treated set

Same outputs as above on Set of patients not treated but with least one blood test or lymph node aspirate test positive

**14.1.8.5: Neurological examination at baseline**

Same outputs as above on Treated set

Same outputs as above on Set of patients not treated but with least one blood test or lymph node aspirate test positive

**14.1.8.6: HAT diagnosis (examination of blood, lymph and CSF samples) at baseline**

Same outputs as above on Treated set

Same outputs as above on Set of patients not treated but with least one blood test or lymph node aspirate test positive

**9.1.2. List of outputs for ICH Section 14.2.1 (Primary efficacy endpoint)****14.2. Efficacy evaluation****14.2.1 Primary efficacy endpoint: outcome at 18 months in stage 2 patients****14.2.1.1 Primary analysis**

14.2.1.1.1: Success rate at 18 months – Stage 2 patients (mITT)

**14.2.1.2 Sensitivity analyses**

14.2.1.2.1: Success rate at 18 months – Stage 2 patients (PPS)

14.2.1.2.2: Success rate at 18 months – Stage 2 patients (Evaluable patients set)

14.2.1.2.3: Success rate at 18 months – Stage 2 patients (Treated set)

14.2.1.2.4: Success rate at 18 months – Stage 2 patients (mITT / fair case method)

14.2.1.2.5: Success rate at 18 months – Stage 2 patients (mITT / best case method)

14.2.1.2.6: Success rate at 18 months – Stage 2 patients (mITT / observed case method)

**14.2.1.3 Forest plot of success rate at 18 months for the yardstick - Stage 2 patients (mITT)**

**9.1.3. List of outputs for ICH Section 14.2.2 (Secondary efficacy endpoints)**

**14.2.2 Secondary efficacy endpoints**

**14.2.2.1 Outcome at 12 months in stage 2 patients**

**14.2.2.1.1 Primary analyses**

14.2.2.1.1.1: Success rate at 12 months – Stage 2 patients (mITT)

**14.2.2.1.2 Sensitivity analyses**

14.2.2.1.2.1: Success rate at 12 months – Stage 2 patients (PPS)

14.2.2.1.2.2: Success rate at 12 months – Stage 2 patients (Evaluable patients set)

14.2.2.1.2.3: Success rate at 12 months – Stage 2 patients (Treated set)

14.2.2.1.2.4: Success rate at 18 months – Stage 2 patients (mITT / fair case method)

14.2.2.1.2.5: Success rate at 18 months – Stage 2 patients (mITT / best case method)

14.2.2.1.2.6: Success rate at 18 months – Stage 2 patients (mITT / observed case method)

**14.2.2.2.2 Outcome at 6 months in stage 2 patients**

Same outputs as above.

**14.2.2.2.3 Outcome at 18 months in stage 1 and intermediate-stage patients**

Same outputs as above.

**14.2.2.2.4 Outcome at 12 months in stage 1 and intermediate-stage patients**

Same outputs as above.

**14.2.2.2.5 Outcome at 6 months in stage 1 and intermediate-stage patients**

Same outputs as above.

**14.2.2.2.6 Outcome at 18 months in intermediate-stage patients**

Same outputs as above.

**14.2.2.2.7 Outcome at 12 months in intermediate-stage patients**

Same outputs as above.

**14.2.2.2.8 Outcome at 6 months in intermediate-stage patients**

Same outputs as above.

**14.2.2.2.9 Outcome at 18 months in stage 1 patients**

Same outputs as above.

**14.2.2.2.10 Outcome at 12 months in stage 1 patients**

Same outputs as above.

**14.2.2.2.11 Outcome at 6 months in stage 1 patients**

Same outputs as above.

**14.2.2.2.12 Overall success rate at 18 months (whatever the stage of HAT)**

14.2.2.2.12.1: Overall success rate at 18 months (mITT, excluding patients with stage 1 and intermediate stage HAT screened before the 20JUN2017)

14.2.2.2.12.2: Overall success rate at 18 months (mITT, weighted by the duration of inclusion of each cohort)

14.2.2.2.12.3: Comparison in success rate at 18-months between stage 1 and intermediate-stage patients versus stage-2 patients (mITT)

14.2.2.2.12.4: Overall success rate at 18 months (mITT)

*Note: as written in section 8.6.2, this table will not be provided if the previous comparison is statistically significant.*

14.2.2.2.12.5: Overall success rate at 18 months giving equal weight to each centre (mITT)

**9.1.4. List of outputs for ICH Section 14.2.3 (Other efficacy endpoints)****14.2.3 Other efficacy endpoints**

14.2.3.1: Changes in the rate of favorable outcomes over time in patients with stage 2 HAT (mITT)

14.2.3.2: Changes in the rate of favorable outcomes over time in stage 1 and intermediate-stage patients (mITT)

14.2.3.3: Kaplan-Meier analysis of time to proven and definitive failure in Patients with Stage 2 HAT (mITT)

14.2.3.3.1: Figure: Kaplan-Meier curve

14.2.3.3.2: Table: Survival probabilities

14.2.3.4: Descriptive analysis and trend test of success rates at 18 months: stage 1 versus intermediate stage versus stage 2 (mITT)

14.2.3.5: Descriptive analysis and trend test of success rates at 12 months: stage 1 versus intermediate stage versus stage 2 (mITT)

14.2.3.6: Descriptive analysis and test of homogeneity of success rates at 18 months by center - Stage 2 patients (mITT)

14.2.3.7 Forest plot of success rate at 18 months by center - Stage 2 patients (mITT)

14.2.3.8: Descriptive analysis and test of homogeneity of success rates at 18 months by center - Stage 1 and intermediate-stage patients (mITT)

14.2.3.9 Forest plot of success rate at 18 months by center - Stage 1 and intermediate-stage patients (mITT)

### 9.1.5. List of outputs for ICH Section 14.2.4 (Exploratory subgroups analysis)

#### **14.2.4: Exploratory subgroups analysis**

14.2.4.1: Descriptive analysis of success rates at 18 months: subgroups A versus B+C+D+E+F (mITT)

14.2.4.2: Descriptive analysis of success rates at 18 months: subgroups A versus B+C+D versus E+F (mITT)

14.2.4.3: Descriptive analysis and trend test of success rates at 18 months: subgroups A vs B vs C vs D vs E vs F (mITT)

14.2.4.1: Descriptive analysis of success rates at 12 months: subgroups A versus B+C+D+E+F (mITT)

14.2.4.2: Descriptive analysis of success rates at 12 months: subgroups A versus B+C+D versus E+F (mITT)

14.2.4.3: Descriptive analysis and trend test of success rates at 12 months: subgroups A vs B vs C vs D vs E vs F (mITT)

### 9.1.6. List of outputs for ICH Section 14.3.1 (Adverse events)

#### **14.3. Safety evaluation**

##### **14.3.1 Adverse events**

###### **14.3.1.1 Overall summary of Adverse events**

14.3.1.1: Overall summary of AEs (Treated set)

###### **14.3.1.2 Adverse events by MedDRA SOC and PT**

14.3.1.2.1: All AEs by MedDRA SOC and PT (Treated set)

14.3.1.2.2: TEAE by MedDRA SOC and PT (Treated set)

14.3.1.2.3: Drug-related TEAE by MedDRA SOC and PT (Treated set)

14.3.1.2.4: Serious TEAE by MedDRA SOC and PT (Treated set)

14.3.1.2.5: Serious drug-related TEAE by MedDRA SOC and PT (Treated set)

14.3.1.2.6: TEAE of interest by MedDRA SOC and PT (Treated set)

